Epinephrine Grade 4: Life-threatening; pressor or ventilatory support indicated Increase monitoring of vital signs as medically indicated until the subject is deemed medically stable in the opinion of the investigator. Hospitalization may be indicated. Subject is permanently discontinued from further trial treatment administration.	•	1 1000010		
Grade 4: Life-threatening; pressor or ventilatory support indicated Increase monitoring of vital signs as medically indicated until the subject is deemed medically stable in the opinion of the investigator. Hospitalization may be indicated. Subject is permanently discontinued from further trial treatment administration.		*		
Life-threatening; pressor or ventilatory support indicated medically indicated until the subject is deemed medically stable in the opinion of the investigator. Hospitalization may be indicated. Subject is permanently discontinued from further trial treatment administration.	Inflitrates)	Epinephrine		
Life-threatening; pressor or ventilatory support indicated medically indicated until the subject is deemed medically stable in the opinion of the investigator. Hospitalization may be indicated. Subject is permanently discontinued from further trial treatment administration.	Grade 4:	Increase menitoring of vital signs as		
ventilatory support indicated deemed medically stable in the opinion of the investigator. Hospitalization may be indicated. Subject is permanently discontinued from further trial treatment administration.	*·			
investigator. Hospitalization may be indicated. Subject is permanently discontinued from further trial treatment administration.		-		
Hospitalization may be indicated. Subject is permanently discontinued from further trial treatment administration.	verillatory support indicated	•		
Subject is permanently discontinued from further trial treatment administration.		· ·		
further trial treatment administration.				
		, ,		

11.6 AE and SAE reporting

11.6.1 Time Period and Frequency of Detecting AEs and SAEs

The investigator or site staff is responsible for detecting, documenting and reporting events that meet the definition of an AE or SAE. See section below for the timeline for reporting SAEs.

AEs and SAEs will be collected from the time the first dose of study treatment is administered until 90 days following discontinuation of study treatment regardless of initiation of a new cancer therapy or transfer to hospice.

After discontinuation of study treatment, the investigator will monitor all AEs/SAEs that are ongoing until resolution or stabilization of the event or until the subject is lost to follow-up. At any time after treatment discontinuation the investigator may report any adverse event that they believe possibly related to study treatment.

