as long as patient is clinically benefitting, is tolerating the drug well and continues to meet all study treatment criteria.

The safety of the combination of epacadostat and pembrolizumab in patients with advanced sarcoma will be determined using CTCAE v4.03 criteria for toxicity assessment. Safety data will be collected for up to 90 days following the last dose of the study drugs. Therapy will be discontinued due to confirmed progression of disease or clinical progression, intercurrent illness that prevents further administration of treatment or intolerance of study treatment. Study personnel will attempt to collect survival status for all patients after the end-of-study visit every 3 months via telephone, email, or another method for up to 1 year.

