Soluble Factors, Serum	Treatment modulation of serum levels of chemokines, cytokines and other immune mediators by ELISA or other multiplex-based assay methods. Primary analysis includes interferon-gamma and IL-10.	Blood Serum (Weeks 1(before treatment), 4, 7, 13, 22 and off-study)
Characterization of Tumor infiltrating lymphocytes	IHC to assess number and composition of immune infiltrates to define immune cell subsets present within	Tumor biopsy at: Baseline

	tumor before and after exposure to treatment. CD3, CD4, CD8 and FOXP3 will be evaluated. 2. Immune cell phenotyping of freshly isolated TIL to evaluate Treg/Teff ratio (CD8+/FoxP3+ cells) and activations markers (ICOS, PD-1, CD69).	Week 7 Progression (optional)
100- 1, PD-L1 & kynurenine expression by IHC	Qualtek immunohistochemistry- based assay for PD-L1	Tumor biopsy at: Baseline Week 7 Progression (optional)
Tumor Biopsy neoantigen analysis	Fresh frozen tumor biopsy will be utilized for massively parallel whole exome sequencing. Available databases such as SNP effect (http://snpeff.sourceforge.neU will be used to determine which mutations are in coding regions and will affect amino acid sequence. NetMHC and the Immune Epitope Database will be utilized to predict MHC Class I binding and T cell interactions, respectively.	Tumor biopsies at baseline Paired normal peripheral blood mononuclear cells at baseline
T-cell receptor sequencing	Highthroughput sequencing of the variable (3 chain of the T-cell receptor.	Tumor biopsy at: Baseline Week 7 Progression (optional)

Table 5. Study calendar -

	Screening	Cycle 1				2	Cycle 3		Off study		
	Screening	Wk1	Wk2	Wk3	Wk4	Wk5	Wk6	Wk7	Wk8	Wk9	visit ¹
EpacadostatA		Х	X	X	Х	Х	Х	Х	Х	Х	
Pembrolizumab ⁸		Х			Х			Х			
Informed consent	Х										
Pathologic Confirmation at study siteJ	x										
Review of concomitant medications	х	х			х			х			
Review of adverse events		х			х			х			x
Physical exam	Х	Х			Х			Х			Х
Routine laboratory testsc	x	х			х			х			Х
Research blood tests ⁰		х			х			х			Х
Hepatitis B, C and HIV	x										
Pregnancy TestE	Х										Х
ECGF	х								Х		Х
ECHO	х										
CT and/or MRI ⁸	х								х		
Biopsy	Х							Х			

- A. Epacadostat will be administered twice daily, orally, continuously from day 1-21 (inclusive) of each treatment cycle, each treatment cycle consists of 21 days
- B. Pembrolizumab will be administered once at a dose of 200mg, intravenously, on day 1 of cycle **1** and every 3 weeks (±3 days) thereafter

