- C. Routine laboratory tests at screening, day 1 of cycle 1 and then prior to every scheduled treatment visit(± 3 days) thereafter. All routine blood samples should be obtained prior to the daily dose epacadostat and/or pembrolizumab. routine laboratory tests include: cbc with differential, PT/INR and a PTT, comprehensive metabolic panel, magnesium and phosphorus, fT4, TSH, T3, lipase and amylase
- D. Research blood samples will be collected at week 1 (before treatment), 4, 7,13, 22 and at the date of the off study visit(± 3 days)

- E. Serum pregnancy test (Female subject of childbearing potential should have a negative serum pregnancy at screening and within 72 hours prior to receiving the first dose of both study drugs and at the off study visit.)
- F. An ECG will be performed at baseline, week 8, every 8 weeks subsequently((± 1 week window) and at the off study visit((± 1 week window)
- G. Standard Imaging studies will be performed at baseline, week 8 and every 8 weeks subsequently (± 1 week window) until 56 weeks, and then every 12 weeks thereafter or as per the discretion of the treating investigator and will include CT of chesUabdomen/pelvis and MRI of the affected area if deemed necessary by the study investigator.
- H. Optional biopsy at progression.
- I. The off study visit will take place 30 days(+/- 7 days) after the last dose of study therapy
- J. Pathologic confirmation of the presence of sarcoma at the study site may take place during or before the screening period.

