11.4.2 Pembrolizumab

Dose reductions - Pembrolizumab

Dose reductions of pembrolizumab are not permitted.

Dose Modification (Escalation/Titration/Other)

Adverse events (both non-serious and serious) associated with pembrolizumab exposure may represent an immunologic etiology. These adverse events may occur shortly after the first dose or several months after the last dose of treatment. Pembrolizumab must be withheld for drug-related toxicities and severe or life-threatening AEs as per table 16 above.

Other allowed dose interruption for pembrolizumab

Dosing interruptions are permitted in the case of medical / surgical events or logistical reasons not related to study therapy (e.g., elective surgery, unrelated medical events, patient vacation, and/or holidays). Subjects should be placed back on study therapy within 3 weeks of the scheduled interruption, unless otherwise discussed with the Sponsor. The reason for interruption should be documented in the patient's study record.

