Upon permanent discontinuation from the study treatment for any reason, the following procedures will be performed approximately 30 (+7) days after the last dose of epacadostat or the last dose of pembrolizumab, whichever is later.

Full medical history, physical exam, assessment of performance status by KPS or ECOG status

Review of concomitant medications

Complete vital signs (pulse, blood pressure, temperature, respiratory rate, oxygen saturation) as well as weight and height. Height may be documented at any time prior to registration.

12-lead electrocardiogram (ECG)

Serum -HCG or urine pregnancy test for women with child-bearing potential. If the urine test is positive or cannot be confirmed as negative, a serum pregnancy test will be required.

Complete blood count with differential, including lymphocyte and eosinophil count.

Comprehensive metabolic panel (glucose, blood urea nitrogen, creatinine, sodium, potassium, chloride, bicarbonate, calcium, total protein, albumin, serum bilirubin, alkaline phosphatase, ASL, AST) phosphorus, magnesium

TSH, T4 free, T3

Amylase and lipase

An optional biopsy will be offered at progression of disease.

Patients whose treatment is interrupted or permanently discontinued due to an adverse event or clinically significant laboratory value must be followed until resolution or stabilization of the event.

Reporting of adverse events will occur for up to 90 days for serious adverse events (within 90 [+7] days after the last administration of epacadostat or pembrolizumab, whichever is later), Events of Clinical Interest (within 90 [+7] days after the last administration of epacadostat or pembrolizumab, whichever is later), and documentation of concomitant medications.

Long-Term Follow-up Procedures:

All subjects who permanently discontinue study drug for any reason other than withdrawal of full consent will be contacted by clinic visit or telephone to assess survival and initiation of additional sarcoma therapy. Contact for all subjects will be attempted every 12 weeks (±28 days) following the safety follow-up visit until death, subject withdraws full consent, or up to 12 months after the end of treatment.

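### Adverse events are to be collected for 90 days after treatment, but the last scheduled adverse-event review is at about day 30

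*Combined protocol and SAP*

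**What the plan says.** **Collection window.** Section 11.6.1 collects AEs and SAEs from the first dose "until 90 days following discontinuation of study treatment regardless of initiation of a new cancer therapy or transfer to hospice". Section 4.1 agrees: "Safety data will be collected for up to 90 days following the last dose of the study drugs". Section 11.6.1 puts the duty to find, record and report events on the investigator or site staff. It has open events followed until they settle, and it permits, without requiring, later reports of possibly related events.

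**Scheduled reviews.** In Table 5 the row "Review of adverse events" is marked at weeks 1, 4 and 7 and at the off-study visit. Note I gives the timing: "The off study visit will take place 30 days(+/- 7 days) after the last dose of study therapy". Section 13 places its post-treatment procedures "approximately 30 (+7) days after the last dose of epacadostat or the last dose of pembrolizumab, whichever is later", and its list of those procedures does not name an AE review.

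**After that visit.** Section 13 states: "Reporting of adverse events will occur for up to 90 days for serious adverse events". It gives ECIs the same 90 [+7] day limit and adds concomitant medications, but attaches no visit or call to the limit. For long-term follow-up it says: "Contact for all subjects will be attempted every 12 weeks (±28 days) following the safety follow-up visit". The stated purpose of that contact is survival and the start of further sarcoma treatment; Section 4.1 mentions survival status only.

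**Other windows.** Section 11.8.2 ends ECI reporting at 30 days if new anticancer therapy starts. Section 17.2 requires SAE reporting for 30 days, and after that only for unexpected events that are at least possibly related.

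**The concern.** A collection window is only as good as the contacts that fill it. Although its title refers to frequency, Section 11.6.1 gives none for the period after treatment, and no other section schedules an AE question after about day 30. A patient who has moved to other care or to hospice, whom Section 11.6.1 explicitly keeps in the window, has no planned occasion on which the study asks about new events.

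Safety is the first secondary objective. The protocol also says of immune-related events on pembrolizumab: "These adverse events may occur shortly after the first dose or several months after the last dose of treatment". A safety table labelled as covering 90 days would then combine about 30 days of scheduled review with about 60 days in which new-onset events are recorded only if they come to the site's notice some other way. With 30 safety-evaluable patients (an assumption; replacements could raise the number), one missed patient-level event shifts a reported incidence by 1/30 = 3.3 percentage points.

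**Working it through.** The plan states no figure for this point, so the check is a day count on its own visit windows. Day 0 is the last dose. I assume that discontinuation (the anchor in Section 11.6.1) and last dose (the anchor in Section 4.1) coincide.

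**Inputs**
- Promised window: 90 days (Sections 4.1 and 11.6.1).
- Last scheduled AE review, at day v: 30 ± 7, so v = 23 to 37 (Table 5, note I). Section 13 gives 30 (+7), so v = 30 to 37.
- Next contact: 84 ± 28 days after that visit (Section 13).

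**Formulas**
- Days without a scheduled AE review = 90 − v.
- Next contact: nominal day v + 84, earliest v + 56, latest v + 112.

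| Visit day v | 90 − v | Share of 90 days | Next contact, nominal | Allowed window |
|---|---|---|---|---|
| 23 | 67 | 74% | day 107 | days 79–135 |
| 30 | 60 | 67% | day 114 | days 86–142 |
| 37 | 53 | 59% | day 121 | days 93–149 |

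Under Table 5 the uncovered span is 53 to 67 days. Under Section 13's window it is 53 to 60 days (59% to 67%). The two visit windows themselves disagree.

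The nominal next contact falls after day 90 in every row. The earliest possible contact (day 79) falls inside the 90 days, but its stated content does not include adverse events.

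**Would a day 90 (+7) contact fit the existing window?** The window opens at v + 56, which is later than day 90 once v exceeds 34. For v up to 34, all of days 90 to 97 is already allowed. For v = 37 the window opens at day 93, so days 90 to 92 would need an amended window.

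**Do the documents' onset figures size the gap?** Section 11.3.1 gives median onset of 5 months for pneumonitis and 6.5 months for colitis. These come from melanoma patients on pembrolizumab alone, with median exposure of 6.2 months (Section 11.3.2), and are not times since last dose. If they are counted from first dose (an assumption, at 30.4 days a month), they are about day 152 and day 198.
- Stop at week 8 (day 56): the gap is study days 86 to 146, and both medians fall after it.
- Stop at week 16 (day 112): the gap is study days 142 to 202, and both fall inside it.

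The result turns entirely on the assumed stopping time. The one onset quoted relative to last dose, a nephritis case 5 months afterwards, lies beyond day 90 in any case.

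**The case against.** The strongest reply is that the plan does not leave these 60 days unattended. Site staff are responsible for detecting events, open events are followed to resolution or stabilization, and SAEs and ECIs must be reported within 90 [+7] days, where the [+7] looks like a visit window. Table 5 is also weak evidence of absence: its columns stop at week 9 plus the off-study visit, and the long-term contacts in Section 13 have no column either. Safety is summarised descriptively, and the primary response endpoint is untouched.

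Much of this stands. A reader might infer that events after day 30 reach the database only if a patient or an outside hospital volunteers them. The documents do not support that, given the site's detection duty and the 90 [+7] day reporting window. What is left is new-onset events, chiefly non-serious ones, since the Section 13 sentence names SAEs, ECIs and concomitant medications rather than all AEs.

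The reply does not close the gap. A duty to detect and a reporting deadline do not create an occasion to ask, and following open events does not find new ones. Nor does the case rest on Table 5 alone: Section 13 spells out the later contacts and gives them a different purpose.

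**Conclusion.** The point holds as a mismatch between the promised window and the schedule. For 53 to 67 of the 90 days after the last dose, no AE review is scheduled, and the next contact is nominally at day 114 (extremes day 79 to 149) with survival and new therapy as its stated content. This rests on reading Table 5 and Section 13 as the full contact schedule.

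Two stronger conclusions are tempting and should not be drawn. One is that late immune events will be under-counted by an amount suggested by the pneumonitis and colitis medians; as shown, those medians do not measure risk after the last dose, and the size of any under-count cannot be computed from the documents. The other is that the loss falls mostly on patients who stop early; no section supports that.

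The conflicting windows in Sections 11.6.1, 11.8.2, 13 and 17.2 add to the problem, because they leave unsettled which events must be captured after day 30. This is worth correcting for the secondary safety analysis and has no bearing on the primary endpoint.

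**What to change.** 1. Time the first long-term contact at day 90 (+7) after the last dose. Amend its window where the off-study visit was late, since after a day-37 visit it now opens only at day 93. Later contacts can stay as planned.
2. Add questions on new AEs, SAEs and concomitant medications, including steroids.
3. List this AE review in Section 13 and in Table 5, name the AE review at the day-30 visit in Section 13, and give that visit one window in both places.
4. Reconcile the collection and reporting windows: 90 days regardless of new therapy (11.6.1), 30 days for ECIs once new anticancer therapy starts (11.8.2), 90 days for SAEs and ECIs (13), and 30 days for SAEs (17.2). Where institutional and company reporting duties really differ, say so, and keep them separate from what is collected for analysis.

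The cost is a slightly longer version of a call already planned; no contact is added. Section 16.3 refers to the study as completed. If follow-up is closed, the safety report should state that scheduled AE review ended at about day 30 and that later events were captured passively.

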11.6.2 Prompt Reporting of Serious Adverse Events and Other Events to MSKCC IRB

Please see section 17.2 for SAE reporting guidelines.

11.6.3 CTCAE term (AE description) and grade

The descriptions and grading scales found in the revised NCI Common Terminology Criteria for Adverse Events (CTCAE) version 4.03 will be utilized for AE reporting. All appropriate treatment areas should have access to a copy of the CTCAE version 4.03. A copy of the CTCAE version 4.03 can be downloaded from the CTEP web site http://ctep.cancer.gov/protocolDevelopmenUelectronic_applications/ctc.htm.

11.6.4 Attribution of the AE:

- Definite The AE is clearly related to the study treatment.
- Probable The AE is likely related to the study treatment.
- Possible The AE may be related to the study treatment.
- Unlikely The AE is doubtfully related to the study treatment.
- Unrelated The AE is clearly NOT related to the study treatment.

11.7 Pregnancy Testing, Prevention and Lactation Reporting

Epacadostat should not be used by pregnant women. Studies to evaluate the potential for embryotoxicity and teratogenicity have not been performed. Pembrolizumab may have adverse effects on a fetus in utero. Furthermore, it is not known if pembrolizumab has transient adverse effects on the composition of sperm.

For this trial, male subjects will be considered to be of non-reproductive potential if they have azoospermia (whether due to having had a vasectomy or due to an underlying medical condition).

The need for a screening pregnancy test depends on whether a female subject is of childbearing potential or non-childbearing potential.

Female subjects will be considered of non-reproductive potential if they are either:

(1) Postmenopausal (defined as at least 12 months with no menses without an alternative medical cause; in women < 45 years of age a high follicle stimulating hormone (FSH)

Memorial Sloan Kettering Cancer Center IRB Number: 17-508 A(8)

Approval date: 07-May-2024

level in the postmenopausal range may be used to confirm a post-menopausal state in women not using hormonal contraception or hormonal replacement therapy. In the absence of 12 months of amenorrhea, a single FSH measurement is insufficient.);

OR

(2) Have had a hysterectomy and/or bilateral oophorectomy, bilateral salpingectomy or bilateral tubal ligation/occlusion, at least 6 weeks prior to screening;

OR

Has a congenital or acquired condition that prevents childbearing.

A female of child-bearing potential is defined as any female who does not meet the criteria of non-childbearing potential as described in the previous paragraph.

If a female subject is of childbearing potential, she must have a serum -HCG or urine pregnancy test performed within 72 hours of the first dose of study treatment. If the urine test is positive or cannot be confirmed as negative, a serum pregnancy test will be required. Subjects with positive pregnancy test result must be excluded from the study.

Female and male subjects of reproductive potential must agree to avoid becoming pregnant or impregnating a partner, respectively, while receiving study drug and for 120 days after the last dose of both epacadostat and pembrolizumab by complying with one of the following:

(1) practice abstinencet from heterosexual activity;

OR

(2) use (or have their partner use) acceptable contraception during heterosexual activity.

Acceptable methods of contraception are+:

Single method (one of the following is acceptable):

- intrauterine device (IUD)
- vasectomy of a female subject's male partner
- contraceptive rod implanted into the skin

Combination method (requires use of two of the following):

- diaphragm with spermicide (cannot be used in conjunction with cervical cap/spermicide)
- cervical cap with spermicide (nulliparous women only)
- contraceptive sponge (nulliparous women only)
- male condom or female condom (cannot be used together)
- hormonal contraceptive: oral contraceptive pill (estrogen/progestin pill or progestinonly pill), contraceptive skin patch, vaginal contraceptive ring, or subcutaneous contraceptive injection

tAbstinence (relative to heterosexual activity) can be used as the sole method of contraception if it is consistently employed as the subject's preferred and usual lifestyle and if considered acceptable by local regulatory agencies and ERCs/IRBs. Periodic abstinence (e.g., calendar, ovulation, sympto-thermal, post-ovulation methods, etc.) and withdrawal are not acceptable methods of contraception.

+If a contraceptive method listed above is restricted by local regulations/guidelines, then it does not qualify as an acceptable method of contraception for subjects participating at sites in this country/region.

Subjects should be informed that taking the study medication may involve unknown risks to the fetus (unborn baby) if pregnancy were to occur during the study. In order to participate in the study subjects of childbearing potential must adhere to the contraception requirement (described above) from the day of study medication initiation (or 14 days prior to the initiation of study medication for oral contraception) throughout the study period up to 120 days after the last dose of trial therapy. If there is any question that a subject of childbearing potential will not reliably comply with the requirements for contraception, that subject should not be entered into the study.

If a female subject is suspected to be pregnant during the study, a serum pregnancy test must be performed. If pregnancy is confirmed, subject must stop study treatment immediately and the pregnancy must be reported. A report confirming a female subject to be pregnant or lactating has to be reported to Incyte and Merck within 24hours of sponsor awareness and submitted within 10 days of sponsor awareness. The site will contact the pregnant subject at least monthly and document the subject's status until the pregnancy has

been completed or terminated. The outcome of the pregnancy will be reported to the study sponsor and to Merck and Incyte without delay and within 24 hours to the Sponsor and within 2 working days to Merck and Incyte if the outcome is a serious adverse experience (e.g., death, abortion, congenital anomaly, or other disabling or life-threatening complication to the mother or newborn). The study investigator will make every effort to obtain permission to follow the outcome of the pregnancy and report the condition of the fetus or newborn to the Sponsor.

